All study bladder instillation mixture will be drawn up in syringes, randomized, and dispensed (given to provider) by one of the medical assistants. The providers will be blinded to the study mixture and will perform the bladder instillations. The bladder instillation ingredients will be prepared in a standardized fashion by a trained medical assistant. The patients will undergo bladder instillations using a standardized technique by a physician or nurse practitioner. The medical practitioner will swab the external urethral meatus with betadine (or other appropriate cleansing agent if patient has an iodine allergy) and then instill approximately 5 mL of 1% viscous lidocaine in the urethra, letting the viscous lidocaine sit for 1 to 10 minutes. A pediatric (8 French) straight-tip catheter will be inserted to drain the bladder and collect a urine specimen for culture if indicated. After the bladder is drained, the bladder will be instilled with either a mixture of triamcinolone acetonide (1 vial, 40 milligrams (mg)/1 milliliters (mL)), heparin (10,000 units), 2% viscous lidocaine (10 mL), 8.4% sodium bicarbonate (15 mL of 1 mEq/mL), and 0.5% bupivacaine (10 mL of 5 mg/mL). After the instillation, the women will lay supine or move from supine to lateral positions intermittently for 20-30 minutes. They will then urinate the instillation. If a patient has previously demonstrated the ability to urinate without difficulty following an instillation, she may depart the office after 20-30 min and urinate the instillation in a more private, non-office setting.

If patients have a reaction to the bladder instillation or desire to stop the instillations, they may do so. Participants will be permitted to obtain any relevant concomitant care and interventions during the trial.

Outcomes

All outcome measures will be collected at 3 weeks into the bladder instillation schedule and again at the completion of the bladder instillations (6 weeks into study participation).

Study Title: Randomized controlled trial comparing two different bladder instillation treatments for interstitial cystitis/bladder pain syndrome.

Primary Outcome:

1. Treatment response as measured by the score of the O'Leary-Sant questionnaire [16,17] as compared between study groups at completion of the bladder instillations.

Secondary Outcomes:

1. O'Leary-Sant subscores (problem and symptom index) at the completion of treatment

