Bladder instillation will be performed weekly with the same mixture that the patient was randomized to (mixture with or without Kenalog) and for 6 weeks. Symptom questionnaires will be given at baseline, 3 weeks, and 6 weeks of treatment. If the patient misses a study appointment, she will be called by telephone and queried about side effects and if appropriate, re-scheduled for an appointment.

We plan to recruit patients from January 2019 until July 2020. Patient follow up will be completed by September 2020. As bladder instillations are commonly performed and considered low risk, no interim analysis will be performed. Urinary tract infection will not be considered an adverse event related to study drug but will be monitored in data collection.

Sample size

Sample size calculation was based on the primary outcome, the O'Leary-Sant score on the final day of bladder instillation treatment as compared between the two treatment groups. Based on previous studies, patients have a baseline IC/BPS score following standard medical treatment of approximately 24 ± 5.6 points.[16,17] A 4.03 point decrease from baseline on the O'Leary-Sant questionnaire corresponds with at least a 50% perceived improvement in the patient's disease.[24] We believe this level of difference between the groups in the final O'Leary-Sant scores would be clinically significant. We want 80% power to detect a 4.03 point decrease from a baseline mean score of 24 (expected score in the bladder instillation without Kenalog group after treatment) with a standard deviation ≤ 5.6 points (alpha 0.05) with a 2-sided t-test. The G*Power sample size calculator was used for the power calculations (<https://www.stat.ubc.ca/~rollin/stats/ssize/n2.html>) and these calculations were confirmed for accuracy by a University of Louisville biostatistician. The resulting sample size was $n= 32$ for each group for a total of 64 enrolled patients. Accounting for a 20% dropout in the study, this would translate to a sample size of 80 patients enrolled with a goal of 40 per group.

Recruitment

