All identifying information and data collected during the course of this study will be kept secure and strictly confidential. All data will be stored electronically on a password protected, encrypted laptop in the possession of the study investigator. Risks for breaches of confidentiality will be minimized by entering data from the medical record to a password protected, encrypted computer database which will have limited access to the PI.

The patient's unique study ID will be used for storage, analysis and publication.

Paper data collections forms will be utilized and data will be entered from the paper data form by a study investigator into either a RedCap database or an encrypted, password protected laptop or computer Excel database. These data forms will be housed in a locked file cabinet in the Division of Female Pelvic Medicine and Reconstruction office in a locked cabinet with restricted access.

Data Analysis and Statistical Methods:

The data will be analyzed in consultation with a department-committed biostatistician utilizing SPSS statistical software. Categorical variables (e.g. 'yes" to certain questions on the PFDI) will be compared using chi-square tests (or Fisher's exact test when appropriate). Continuous variables (such as primary outcome) will be compared using t-tests, and changes in continuous outcomes over time (e.g. change from baseline to 8-week O'Leary-Sant score) will be compared with paired t-tests. A regression analysis will be performed to determine the impact of various relevant cofactors (e.g. patient age, presence of other chronic disorders, level of OAB symptoms) on the relationship between group assignment and treatment outcomes.

We will perform an intention-to-treat analysis by the assigned study groups for the initial analysis, comparing women who followed up at the completion of the study (6-week outcomes) between the study groups (bladder instillations with and without Kenalog) as

Study Title: Randomized controlled trial comparing two different bladder instillation treatments for interstitial cystitis/bladder pain syndrome.
assigned. We will also perform a per-protocol analysis, comparing women in the bladder instillation with Kenalog who had at least 4 bladder instillation treatments to the group that had bladder instillations without Kenalog. Lastly, we will perform two types of sensitivity analysis:

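### The primary t-test on the final O'Leary-Sant score ignores the baseline score; a baseline-adjusted model would gain precision and power at almost no cost

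*Combined protocol and SAP*

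**What the plan says.** Under Primary Outcome, treatment response is the O'Leary-Sant score "as compared between study groups at completion of the bladder instillations". The Sample size section uses the same endpoint, the "score on the final day of bladder instillation treatment as compared between the two treatment groups", and calculates the number needed "with a standard deviation ≤ 5.6 points (alpha 0.05) with a 2-sided t-test". Data Analysis and Statistical Methods then gives the test: "Continuous variables (such as primary outcome) will be compared using t-tests". No covariate is attached to it.

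The baseline value is available. The Participant timeline states: "Symptom questionnaires will be given at baseline, 3 weeks, and 6 weeks of treatment". The Eligibility criteria also use the questionnaire as the entry test, with a score of at least 6 on either index.

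Three other parts of the plan touch on baseline or covariates:

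- **Regression.** Data Analysis and Statistical Methods plans a regression on cofactors. Its examples are age, other chronic disorders and level of OAB symptoms. The baseline O'Leary-Sant score is not among them, and the regression is not designated primary.
- **Change from baseline.** This is a secondary outcome, and changes over time are assigned to paired t-tests.
- **Randomisation.** Sequence generation describes permuted blocks with 1:1 allocation. It mentions no stratification by severity.

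**The concern.** Women can enter with a score as low as 6 on one index, with no upper limit, so they may differ considerably in severity before treatment. If severity at entry predicts severity at six weeks, an analysis of final scores alone leaves that predictable variation in the error term. The confidence interval is then wider, and power lower, than the collected data allow.

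A chance difference between arms at baseline also passes partly into the estimated treatment effect. With about 32 women analysed per arm and no stratification on severity, such a difference need not be trivial beside a target of 4.03 points. These are two views of the same excess variance, not separate harms.

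There is a practical side too. The cofactor regression is open-ended, so the baseline score could be added to it later. If that happened after results were known, the adjusted estimate would look chosen rather than planned.

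**Working it through.** **Inputs from the Sample size section.** Difference 4.03 points; SD 5.6 (stated as an upper limit); two-sided alpha 0.05; target power 80%; 32 evaluable per arm; 20% dropout; 80 enrolled.

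**Assumed input.** The correlation r between baseline and 6-week total score is not in the documents, so it is varied from 0 to 0.7.

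**Step 1: reproduce the plan's figure.** The standardised difference is 4.03/5.6 = 0.72. With the exact two-sample t-test (noncentral t), power is 79.6% at 31 per arm and 80.9% at 32, so 32 per arm is right. Allowing for dropout, 64/0.80 = 80. The plan's numbers reproduce.

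**Step 2: precision of the planned analysis.** The standard error of the difference is 5.6 × √(2/32) = 1.40 points. The 95% CI half-width is 2.00 × 1.40 = 2.80 points (t quantile on 62 degrees of freedom).

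**Step 3: precision with baseline adjustment.** The residual SD is 5.6 × √(1 − r²), with 61 degrees of freedom. The variance of the treatment estimate falls by about r². At 32 per arm and a true difference of 4.03:

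| r (assumed) | Residual SD | Power | 95% CI half-width |
|---|---|---|---|
| 0 | 5.60 | 80.9% | 2.80 |
| 0.2 | 5.49 | 82.4% | 2.74 |
| 0.3 | 5.34 | 84.4% | 2.67 |
| 0.4 | 5.13 | 87.1% | 2.57 |
| 0.5 | 4.85 | 90.5% | 2.42 |
| 0.6 | 4.48 | 94.3% | 2.24 |
| 0.7 | 4.00 | 97.8% | 2.00 |

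The difference detectable with 80% power is 3.98 points for the t-test. With adjustment it is 3.80, 3.45 or 2.85 points at r = 0.3, 0.5 or 0.7.

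**Step 4: check by simulation (40,000 trials per setting, normal data).** Type I error was about 5% for both methods. Power for the t-test was about 81% throughout. For ANCOVA it was 80.4%, 83.9%, 90.1% and 97.7% at r = 0, 0.3, 0.5 and 0.7. The small shortfall from the table arises because the formula ignores the slight cost of estimating the baseline slope. At r = 0 that cost is about half a percentage point.

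**Step 5: chance imbalance.** If the baseline SD is also 5.6, the difference in baseline means has SE 1.40. The chance that the arms start at least 1.40 points apart is then 32%, about one trial in three. An imbalance of that size moves the unadjusted estimate by r × 1.40, which is 0.42, 0.70 or 0.98 points at r = 0.3, 0.5 or 0.7.

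**Step 6: would the change score serve instead?** A between-arm t-test on change from baseline had simulated power of 67%, 81% and 96% at r = 0.3, 0.5 and 0.7, below ANCOVA each time. The paired t-tests in the plan assess change within women and do not compare the arms.

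**Step 7: if the SD is larger than planned.** Taking 6.5 as an illustration (assumed), t-test power at 32 per arm falls to 68.5%. ANCOVA gives 72.5% at r = 0.3 and 80.5% at r = 0.5.

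**The case against.** The strongest reply is that nothing here is wrong. Under 1:1 randomisation a t-test on final scores is valid. It matches the stated endpoint and the sample-size method, and it meets its 80% target on the plan's own inputs. Chance imbalance is already reflected in its standard error. All of that stands: this is a loss of efficiency, not a bias or an error in N.

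A second reply is that the benefit depends on a correlation the documents do not supply. It could be low, and selecting women on a score threshold could lower it further. That also stands. At r = 0.2 the gain is only about 1.5 percentage points of power, so the direction is secure but the size is not.

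Third, the 5.6 comes from earlier studies of women after standard medical treatment, so using it as the baseline SD of the women enrolled here is an assumption. That is fair, although the Sample size section itself presents 24 ± 5.6 as a baseline score. Nor does adjustment remove chance imbalance in general; it accounts only for imbalance in the baseline O'Leary-Sant score.

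Fourth, the regression's cofactor list is illustrative and could include the baseline score. It could, but nothing commits the investigators to it, and the t-test would still be the primary analysis.

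Finally, only the O'Leary-Sant total was examined numerically. Extending the adjustment to the secondary questionnaires rests on the same reasoning, not on separate figures.

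**Conclusion.** The concern holds. The primary analysis leaves unused a baseline measurement that every participant provides, and no other part of the plan makes a baseline-adjusted comparison of the arms primary. For a plausible middle value, r = 0.5, adjustment would raise power from 80.9% to 90.5% and narrow the 95% CI half-width from 2.80 to 2.42 points, a 25% cut in variance. Over r = 0.3 to 0.7 the variance reduction runs from 9% to 49%. If r is near zero the two analyses perform almost identically.

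These figures assume 32 evaluable women per arm, an SD of 5.6 and a linear relation between baseline and final score. The imbalance figures also assume a baseline SD of 5.6. The plan should be changed, but the trial as designed is not invalid without the change.

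**What to change.** State in Data Analysis and Statistical Methods that the primary test is the arm coefficient, with 95% CI and two-sided alpha 0.05, from a linear model of the 6-week total O'Leary-Sant score on randomised arm and baseline total score. Keep the unadjusted t-test as a supportive analysis. For each secondary questionnaire score at six weeks, compare the arms with the same model, using that questionnaire's own baseline score.

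Write this in before the allocation is unblinded. Leave enrolment at 80: a smaller number should not rest on a correlation nobody has verified, and the added precision is useful if the SD exceeds 5.6.

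The cost is one sentence in the plan and one degree of freedom. No new data, visits or patients are needed, and the planned software (SPSS) fits the model.

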The patients, once consented, will be randomly assign to a treatment group by using the randomization sequence that was created by an uninvolved statistician. The patients will use their SIDNs for the remainder of the study. They are blinded to treatment because the study medications all look the same except for the syringe labeling with the patient's SIDN. All patients will otherwise receive the same treatment and care.

The investigators are blinded because they are not privy to the bladder instillation mixture that the patient was assigned to and all patients are otherwise treated and assessed the same.

Unblinding (unmasking)

Should unblinding be warranted such as in exceptional circumstances when knowledge of the actual treatment is absolutely essential for further management of the patient, the ULH biostatistician who has access to patient allocation, will be contacted to disclose to the principal investigator (PI) which treatment group the affected participant was assigned. The incident will be submitted on a case report form.

Methods: Data collection, management, and analysis

Study Title: Randomized controlled trial comparing two different bladder instillation treatments for interstitial cystitis/bladder pain syndrome.

Data collection methods

All information will be obtained directly from questionnaires completed by the patient at the initial study visit, from contact points during study visits at which bladder instillations, are being performed, or at the end of the study at the 6th bladder instillation. The patients will undergo bladder instillations at the University of Louisville Female Pelvic Medicine clinics either at the Spring Clinic location or the HCOC building, and data from validated questionnaires and medication compliance worksheets will be collected on paper at the appropriate time point. Data will be extracted and entered into a RedCap or password-protected Excel spreadsheet as outlined below. No data will be extracted from the patient's medical record or HCOC AllScripts electronic medical record system for this study; all data will be collected directly via study questionnaires and data report sheets designed for use in this study.

Retention and follow-up

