We plan to query adverse events or side effects at each study visit. We offer appointments three days a week to allow for optimal scheduling and will call patients if they are unable to make their follow up visit to ask about medication side effects as well as reschedule them for another appointment time. They will be given written and verbal instructions on what to do in the event of side effects or adverse events to increase the likelihood of them presenting in person and communicating with their physician and/or study investigators about any issues. Patients will be allowed to submit their interval and end-of-study questionnaires during their appointment visits.

Data Management

Data collection form: See below and Appendix A

The following information will be collected directly from study questionnaires and entered into an encrypted excel spreadsheet:

- Study ID number (SIDN)
- Name
- Date of birth
- Age
- Race/ethnicity
- Contact information
- Emergency contact information (if patient willing to provide)
- Social security number (SSN)
- Weight
- Body mass index (BMI)
- Smoking status
- Gravidity
- Parity

Study Title: Randomized controlled trial comparing two different bladder instillation treatments for interstitial cystitis/bladder pain syndrome.

- Reason for visit
- Prior pelvic reconstructive surgery
- Medical history, specifically history of: irritable bowel syndrome, fibromyalgia, chronic pain, chronic pelvic pain, vulvodynia, anxiety, depression, chronic fatigue syndrome
- Charleston comorbidity index[25]
- O'Leary-Sant questionnaire (problem and symptom index scores)[16,17]
- Pelvic pain and urgency/frequency (PUF) questionnaire[18]
- Overactive Bladder Questionnaire (OABq)[19]
- Pelvic floor distress inventory (PFDI)[20]
- Sexual function measured by the Pelvic Organ Prolapse Incontinence Sexual Questionnaire, IUGA-Revised (PISQ-IR) questionnaire[21-23]
- Visual Analogue Scale (VAS) for pain
- Timing and nature of adverse events during the study, regardless of suspected or known relationship to study medication

Data Handling/Storage:

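### The analysis called intention-to-treat is a complete-case analysis by assigned arm, and no procedure is described for obtaining a week-6 score after a woman stops instillations

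*Combined protocol and SAP*

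**What the plan says.** Under Data Analysis and Statistical Methods, the initial analysis is named intention-to-treat, by assigned group, and defined as "comparing women who followed up at the completion of the study (6-week outcomes) between the study groups". The same section adds a per-protocol analysis "comparing women in the bladder instillation with Kenalog who had at least 4 bladder instillation treatments" with the other arm. It then lists three single imputations for missing data: baseline carried forward, best available value, and most recent available value.

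The Sample size section plans for loss: "Accounting for a 20% dropout in the study, this would translate to a sample size of 80 patients enrolled".

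On stopping, the Interventions section says: "If patients have a reaction to the bladder instillation or desire to stop the instillations, they may do so".

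On collection:
- Data collection methods takes all information from the initial visit and then from "contact points during study visits at which bladder instillations, are being performed, or at the end of the study at the 6th bladder instillation".
- Retention and follow-up says: "Patients will be allowed to submit their interval and end-of-study questionnaires during their appointment visits".
- After a missed appointment, the Participant timeline says "she will be called by telephone and queried about side effects and if appropriate, re-scheduled for an appointment". Neither this text nor the similar text under Retention and follow-up mentions an outcome questionnaire.
- The Outcomes section has measures collected at 3 weeks and "again at the completion of the bladder instillations (6 weeks into study participation"), which ties the final measure both to the end of treatment and to elapsed time.

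**The concern.** Two things combine. First, the label does not match the set analysed: keeping women in their assigned arm is one half of intention-to-treat, and including all those randomised is the other. Second, the gap begins at data collection. Every described collection point after baseline is an instillation visit, an appointment or the sixth instillation. A woman who wants no further instillations has no described way to supply a week-6 score.

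If the plan is followed as written, dropout by arm, baseline scores, any week-3 scores and adverse events will be visible. The stoppers' week-6 scores, which determine the bias, will not. The primary estimate would be reported as intention-to-treat while describing only women with 6-week data, and later analysis cannot restore scores that were never collected.

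**Working it through.** **The plan's own figures.** Inputs from the Sample size section: difference 4.03, SD 5.6, two-sided alpha 0.05, 80% power, 20% dropout. The noncentral t gives power 0.796 with 31 per arm and 0.809 with 32, so 32 per arm (64 in total) is reproduced. Then 64 / (1 − 0.20) = 80 enrolled, 40 per arm, and 80 − 64 = 16 women may lack a week-6 score.

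**Bias formula.** Let p be an arm's dropout share and δ the amount by which stoppers' week-6 mean exceeds completers' (higher is worse). An arm's all-randomised mean is its completer mean + pδ. With the same δ in both arms, the complete-case difference (Kenalog minus control) departs from the all-randomised difference by (p_control − p_Kenalog) × δ. The documents give neither dropout by arm nor δ; both are assumed below.

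| Dropout | δ = 4 | δ = 2 to 6 |
|---|---|---|
| 20% vs 20% | 0 | 0 |
| 25% vs 15% | 0.10 × 4 = 0.4 | 0.2 to 0.6 |
| 30% vs 10% | 0.20 × 4 = 0.8 | 0.4 to 1.2 |

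The arm with more dropout looks better, whichever arm that is. Equal dropout alone does not guarantee zero: at 20% in each arm with δ = 4 in one arm only, the bias is 0.20 × 4 = 0.8.

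**Two cases that must be kept apart.**

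*Case 1: all-randomised means equal, so completers differ.* By the noncentral t with SD 5.6, the complete-case test rejects in:
- 5.9% of trials at 25% vs 15% (30 vs 34 women, shift 0.4; 5.2% to 7.1% for δ = 2 to 6)
- 8.6% of trials at 30% vs 10% (28 vs 36 women, shift 0.8; 5.9% to 13.3%)

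*Case 2: completers equal, so all-randomised means differ.* The false-positive rate is not inflated: completers share one mean and SD, so the test rejects at about 5% (4.6% and 4.8% in simulations of the two scenarios below). The fault here is that the estimate misses a difference of about 0.8.

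**Whether the planned imputations repair Case 2.** Simulation of 4,000 trials, 40 per arm, dropout 10% Kenalog and 30% control. Assumed: correlations 0.5 (baseline with week 3 and with week 6) and 0.6 (week 3 with week 6); 30% of stoppers leave before week 3; week-3 change is half the week-6 change. Monte Carlo error is about 0.02. Entries are Kenalog minus control.

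| Analysis | (a) Completers improve 4, stoppers unchanged | (b) Completers unchanged, stoppers worsen 4 |
|---|---|---|
| All randomised | −0.81 | −0.77 |
| Complete-case | −0.01 | 0.04 |
| Baseline carried forward | −0.81 | 0.01 |
| Most recent value | −0.80 | −0.26 |
| Best value | −0.49 | 0.21 |

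In (a) the two carried-forward analyses recover the all-randomised difference. In (b) none of the three does, and best value has the wrong sign. Best value takes the lower of two noisy scores, which flatters the arm with more dropout.

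**Effect of collecting stoppers' scores.** If a share r of stoppers' scores is obtained at random, an arm's observed mean shifts by δ × pr / (1 − p + pr). For 30% vs 10%, δ = 4, r = 0.5: 4 × (0.1765 − 0.0526) = 0.495, leaving a bias of 0.80 − 0.495 = 0.305.

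| Share obtained | 30% vs 10% | 25% vs 15% |
|---|---|---|
| None | 0.80 | 0.40 |
| Half | 0.305 | 0.153 |
| Three quarters | 0.135 | 0.068 |
| All | 0 | 0 |

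Unequal recovery creates its own bias: 75% vs 50% obtained at 20% dropout in each arm gives 4 × (0.15/0.95 − 0.10/0.90) = 0.19.

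**The case against.** The plan states openly whom it compares, keeps women in their assigned arm, and pre-specifies three analyses that return dropouts to the comparison. A reader might infer that missing data are ignored; they are not, and in scenario (a) two of the three analyses work. This narrows the point but does not answer scenario (b) or the label.

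A reader might also infer that the plan excludes women who stop. It does not say so. The Outcomes section dates completion as six weeks of participation, the per-protocol cut at four instillations suggests that some women with fewer may have final scores, and submission at visits is worded permissively. The consent form and worksheets listed under Appendices are not in the text reviewed, so a procedure there cannot be ruled out. What stands is that the protocol text permits a week-6 score after stopping but describes no means of obtaining it.

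Finally, the sizes rest on assumptions. Patients and providers are blinded and care is otherwise the same, which makes balanced dropout more plausible. If true dropout is 20% in both arms, a gap of 8 or more women (such as 12 vs 4) arises by chance in about 3.5% of trials. That is a fair reason not to expect the larger figures. Blinding does not guarantee balance, however, if Kenalog itself changes symptoms or tolerability.

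**Conclusion.** The point holds. The primary analysis is complete-case by assigned arm, may omit up to 16 of 80 randomised women, and lacks a described procedure for scores after stopping. It should be fixed.

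The size and direction of bias are unknown. Under the assumed figures (stoppers 4 points worse, SD 5.6, 40 per arm) it is 0.4 to 0.8 points for the two unequal-dropout patterns shown. A reader might infer that the trial's false-positive rate is inflated. That follows only if all-randomised means are equal while dropout, or stoppers' prognosis, differs by arm, and the documents give no evidence of either. Nor would a 0.8-point bias overturn a result at the target: with 28 versus 36 women the critical difference is 2.82, and 4.03 − 0.80 = 3.23 still exceeds it.

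**What to change.** 1. Amend Interventions, Outcomes, Data collection methods, and Retention and follow-up so that the week-6 O'Leary-Sant score is sought from every randomised woman, whether or not she is still receiving instillations, by telephone, mail or REDCap. The collector should be blinded to allocation, so not the medical assistant who prepares the mixtures. Record the mode and the share obtained by arm, and include these scores in the primary comparison by assigned arm.
2. Label any analysis limited to women with 6-week data complete-case.
3. For scores still missing, add a delta-adjusted (tipping-point) analysis beside the three planned imputations, with deltas varied separately by arm. Each 1-point delta moves the estimate by that arm's missing share. With 20% missing in each arm, deltas of 0 to 6 span −1.2 to +1.2 (0.20 × 6).

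Cost: an amendment, modest extra analysis work, and a scheduled week-6 contact for women who have stopped. The existing call does not cover this, because only a missed appointment triggers it. Contact details are already retained for questionnaire queries (Confidentiality). Some scores will come by a different mode, and partial or unequal recovery leaves some bias. The all-randomised effect may also be smaller: if 20% stop and gain nothing (assumed), it is 0.8 × 4.03 = 3.22.

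### The per-protocol analysis sets a four-instillation minimum for the Kenalog arm only, so the two arms are selected differently after randomisation

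*Combined protocol and SAP*

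**What the plan says.** Data Analysis and Statistical Methods puts an intention-to-treat analysis first, "comparing women who followed up at the completion of the study (6-week outcomes) between the study groups" as assigned. It then adds a per-protocol analysis, in which the sets to be compared are "women in the bladder instillation with Kenalog who had at least 4 bladder instillation treatments to the group that had bladder instillations without Kenalog". The clause about four treatments qualifies the Kenalog women. The comparator is described only by its mixture, and no other section defines a per-protocol set.

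The rest of the protocol treats the arms alike:

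- Participant timeline: "Bladder instillation will be performed weekly with the same mixture that the patient was randomized to (mixture with or without Kenalog) and for 6 weeks".
- Interventions: "If patients have a reaction to the bladder instillation or desire to stop the instillations, they may do so".
- Blinding (masking): "All patients will otherwise receive the same treatment and care".

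Two further statements decide who can have a final score. Data collection methods takes data from the initial visit, from the instillation visits, "or at the end of the study at the 6th bladder instillation". Retention and follow-up states: "Patients will be allowed to submit their interval and end-of-study questionnaires during their appointment visits".

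**The concern.** The number of instillations a woman receives is known only after randomisation and may be related to how she is doing. Screening one arm on it and not the other breaks the comparability that randomisation gave. The Kenalog set loses its under-treated women and the control set keeps them.

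This bears on the trial's own question, which is whether the steroid adds anything to a mixture whose other agents are also expected to help. A one-arm minimum ensures reasonable exposure to those shared agents in the Kenalog set only. A per-protocol result is normally read as a check on the intention-to-treat result. Here, a difference between the two could come from the selection rule and not from Kenalog.

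**Working it through.** **Scale, from the plan's own figures.** The Sample size section gives a target difference of 4.03 points, SD 5.6, two-sided alpha 0.05 and 80% power. A two-sample t-test needs 31.3 per group, rounded up to 32 (power 0.809). Then 64 / 0.8 = 80, matching "Accounting for a 20% dropout in the study, this would translate to a sample size of 80 patients enrolled". These figures are not in dispute and serve only as the scale.

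**Inputs the documents do not give (assumed).**

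- *p*: share of each arm with fewer than four instillations.
- *r*: share of those women who still give a 6-week score.
- *δ*: how much worse (higher) their final score is.

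**Bias.** Suppose there is no true Kenalog effect, stopping is identical in both arms, and every other woman is observed. Let *m* be the mean final score of women with at least four instillations. The filtered Kenalog set has mean *m*. The unfiltered control set has mean *m* + *δw*, where *w* = *pr* / (*pr* + 1 − *p*). The spurious benefit to Kenalog is therefore *δw*.

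**Case 1: 40 randomised per arm, *p* = 20% (8 women per arm), total SD 5.6.** Type I error is from simulation (100,000 replicates, pooled two-sided t-test at 0.05).

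| r | w | Bias, δ = 4 | Type I | Bias, δ = 6 | Type I |
|---|---|---|---|---|---|
| 0 | 0 | 0 | 5.0% | 0 | 5.0% |
| 25% | 0.05/0.85 = 0.059 | 0.24 | 5.2% | 0.35 | 5.9% |
| 50% | 0.10/0.90 = 0.111 | 0.44 | 6.2% | 0.67 | 7.8% |
| 75% | 0.15/0.95 = 0.158 | 0.63 | 7.6% | 0.95 | 11.0% |
| 100% | 0.20/1.00 = 0.200 | 0.80 | 9.0% | 1.20 | 15.1% |

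Hand check of the last row at δ = 4: 32 Kenalog women against 40 controls gives SE = 5.6 × √(1/32 + 1/40) = 1.33. The shift is 0.80 / 1.33 = 0.60 SE. Type I error ≈ Φ(−1.96 + 0.60) + Φ(−1.96 − 0.60) ≈ 0.087 + 0.005 = 0.092, in line with the simulated 9.0%.

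**Case 2: 32 women per arm with a 6-week score, before the per-protocol filter.** Here *q* is the share of those women with fewer than four instillations, on top of the planned 20% dropout. Bias = *q* × *δ*.

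| q | δ | Bias | Type I |
|---|---|---|---|
| 5% | 4 | 0.2 | 5.3% |
| 10% | 2 | 0.2 | 5.1% |
| 20% | 4 | 0.8 | 8.1% |
| 20% | 6 | 1.2 | 12.6% |
| 30% | 6 | 1.8 | 21.8% |
| 20% | 0 | 0 | 5.0% |
| 20% | −4 | 0.8 against Kenalog | 8.1% |

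**Same minimum in both arms.** Simulated bias is about 0 and type I error 4.8% to 5.1% in all these scenarios. That result depends on the assumption that stopping works identically in the two arms.

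**The case against.** **The sentence may be elliptical.** The four-treatment minimum may have been meant for both arms. The surrounding text is loosely drafted: the same section announces two types of sensitivity analysis and lists three, and it mentions an 8-week score in a 6-week study. This is plausible, but no passage confirms it. Two analysts could build different sets from the sentence, so it needs rewording under either reading.

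**Early stoppers will mostly have no final score.** Final data are tied to the sixth instillation and questionnaires to appointment visits. A woman who stops before her fourth treatment would usually drop out of either arm, which is the *r* = 0 row, with no bias. A rescheduled visit would also tend to raise her count toward four. This is the strongest point, and it makes the small-bias rows more credible than the large ones. It does not close the matter. The Outcomes section also times the final measurement at six weeks of participation, and missed visits can be rescheduled, so some under-treated women may be scored. The imputation analyses do not say which set they cover. Applied to the per-protocol set, they would bring in under-treated controls who have no 6-week score.

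**The upper scenarios are extreme.** In Case 2, *q* = 30% means 8 women lost plus 0.30 × 32 = 9.6 under-treated, or 17.6 of 40 (44%). At *q* = 20% it is 8 + 6.4 = 14.4 of 40 (36%). This stands, and the 21.8% figure should be read as an outer bound.

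**Consequence and remedy are limited.** No sample size or success criterion rests on the per-protocol result. A symmetric rule is also still a post-randomisation selection, and bias can remain if reasons for stopping differ by arm. Both points stand. They limit the importance of the finding but do not justify a one-arm rule.

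**Conclusion.** The concern holds: the rule is wrong as written. The minimum is attached to one arm, nothing in the design justifies the asymmetry, and the resulting comparison can be biased.

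The size cannot be fixed from the documents. At *p* = 20% and a 4-point gap, the bias runs from 0 to 0.80 points. The top value is 0.80 / 4.03 = 20% of the target difference. Type I error runs from 5.0% to about 9.0%, depending on how many under-treated women give a final score. The bias favours Kenalog if under-treated women score worse, vanishes if they score the same or none is scored, and reverses if they stopped because they had improved.

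The damage is confined to a supportive analysis. The point should be corrected, but it does not threaten the trial's main conclusion.

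**What to change.** Replace the per-protocol sentence with wording such as:

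> We will also perform a per-protocol analysis comparing women in each arm who received at least 4 of their assigned bladder instillations.

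Report for each arm the number of women excluded by this rule and how many of them had a 6-week score. That shows how much selection remains and whether it differs between arms. Make the change before the allocation is unblinded.

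The cost is one sentence and slightly fewer control women in a supportive analysis. If a symmetric rule was intended all along, the new wording only confirms it. Treatment, visits and data collection do not change.
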